5. STUDY PROCEDURES

Potentially eligible subjects will be screened by one of the investigators by asking patients to rate their worst oral pain or pain score (0-10) over the previous week (see Appendix). Those answering with at

CONFIDENTIAL

This document is confidential. Do not disclose or use except as authorized.

least a score of “7” (1/10) and that meet all other eligibility requirements (see Section 3) will be eligible for enrollment. All patients will sign informed consent for study participation. Each study visit is anticipated to take approximately 45 minutes. A urine pregnancy test will be performed for women of child bearing potential.

There is no financial compensation for participating in this study. Treatment will be administered on an outpatient basis. Study medication will be prescribed by authorized study staff physicians and filled by the BWH Investigational Pharmacy at no expense for the patient. No investigational or commercial agents or therapies other than those described below may be administered with the intent to treat the participant’s oral lichen planus.

Subjects will be evaluated clinically at baseline before starting treatment and at the end of the four-week period, for a total of two visits. Comprehensive subjective and objective data will be collected (Appendix 3 & 4) and intraoral photographs will be obtained. Oral mucosal disease will be evaluated using both patient reported (questions/visual analog scales) and clinician assessed measures.

Subjects will be prescribed compound dexamethasone 0.5mg/5ml solution in Mucolox™ (ARM A) or dexamethasone 0.5mg/5ml solution only (ARM B). All subjects will also receive a prescription for fluconazole 200 mg tablets once-a-week as prophylactic antifungal therapy. Any subjects that are already taking an antifungal oral medication at the time of the study enrollment will continue their prescribed medication and will not need to take the additional weekly fluconazole dose. Subjects will return for evaluation after four weeks at which time the study end-points will be assessed.

Clotrimazole or Nystatin will be prescribed as an alternative antifungal drug in the event of fluconazole allergy.

If there is worsening of oral lichen planus that requires initiation of new immunomodulatory medications (systemic or topical), patients will remain on treatment, but will be regarded as unevaluable for the primary endpoint.

	Day 1 (baseline)	Day 28 ± 5 days (end of study)
Clinical examination	x	x
COMDQLQ	x	x
Patient Reported Outcomes	x	x

5.1.1 Clinician Reported Outcomes

Mucosal disease will be measured using the REU scoring system for monitoring oral lichen planus³⁰. Assessment requires only a light source and a dental mirror. This is a validated semiquantitative instrument for monitoring reticular/hyperkeratotic, erosive/erythematous, and ulcerative OLP lesions. The oral cavity is divided into ten sites: right buccal mucosa, left buccal mucosa, tongue dorsum, tongue ventrum, maxillary gingiva, mandibular gingiva, floor of mouth, hard palatal mucosa, soft

CONFIDENTIAL

This document is confidential. Do not disclose or use except as authorized.

palate and tonsil, and labial mucosa (upper and lower together). The severity of each type of lesion is scored according to the presence or absence of reticulations/hyperkeratosis (0 = absent; 1 = present), and the size of the erosions/erythema or ulcers (in cm²) (0 = no involvement; 1-3 in increasing area of involvement). Because each type of lesion causes different degrees of discomfort and pain, each type of lesion is weighted accordingly: reticular lesions are weighted 1 because this presentation tends to be asymptomatic; erosive/erythematous lesions are weighted 1.5 since they tend to cause some degree of discomfort; ulcerative lesions are weighted 2.0 since they tend to be the most painful. The scores for each site are then totaled.

Intraoral photographs will be obtained at each visit.

5.1.2 Chronic Oral Mucosal Diseases Quality of Life Questionnaire

Patients will complete the 24-item Chronic Oral Mucosal Diseases Quality of Life Questionnaire (COMDQLQ) instrument at baseline and at the end of treatment³¹. This is a validated instrument that assesses various aspects of oral health and function that has been shown to perform well in patients with oral mucosal diseases, including oral lichen planus.

5.1.3 Patient Reported Outcomes

Subjective assessments of subjects' oral symptoms will be obtained by using instruments from the NIH consensus documents for oral cGVHD, a condition that is very similar to oral lichen planus (see Appendix 2&4). These include report of mouth sensitivity at rest and sensitivity with stimulation (e.g. eating) on an eleven point scale. For the primary endpoint the worst sensitivity in the past week will be used. The clinician seeing the subject will complete these forms at each study visit. Patients will also report daily sensitivity on an eleven point scale (see Treatment diary). Tolerability and compliance will also be evaluated, and a patient reported global assessment of overall improvement will be evaluated at the four-week visit.

5.2 Treatment Regimen

A four week supply of compound dexamethasone 0.5mg/5ml solution in Mucolox™ (Arm A) and dexamethasone 0.5mg/5ml solution (Arm B) will be dispensed. The treatment instructions will be to rinse and spit (NOT swallow) with one teaspoon (5 mL) of solution, three times a day for 5 minutes at a time, and not to eat or drink for 15 minutes afterwards. Subjects will maintain a diary and record each dose, the length of time rinsing, and any adverse effects (e.g. transient burning).

Regimen Description						
	Agent	Premedications; Precautions*	Dose	Route	Schedule	Cycle Length
Arm A	Dexamethasone in Mucolox™	None	5mL x 0.1mg/mL = 0.5 mg/rinse, 3 times/day =1.5 mg	Oral Rinse, 5 mins. each time (do not swallow)	7 days/week	28 days (4 weeks) One Cycle Only*

CONFIDENTIAL

This document is confidential. Do not disclose or use except as authorized.

Arm B (standard of care)	Dexamethasone solution	None	5mL x 0.1mg/mL = 0.5 mg/rinse, 3 times/day =1.5 mg	Oral Rinse, 5 mins. each time (do not swallow)	7 days/week	28 days (4 weeks) One Cycle Only*

*All subjects will be treated with antifungal dosing for prophylaxis (see section 5.5)

5.3 Study Agents Administration

The Investigator or co-investigators will prescribe the study drug in the clinic via Epic and instruct the patient on study drug use. Both dexamethasone compound 0.5mg/5ml solution in Mucolox™ and dexamethasone solution will be dosed topically at a concentration of 0.5 mg/5mL.

A four week supply will be dispensed. The treatment instructions will be to rinse and spit (NOT swallow) with one teaspoon (5 mL) of the solution, three times a day for 5 minutes at a time, and not to eat or drink for 15 minutes afterwards. Subjects will maintain a diary and record each dose, the length of time rinsing, and any adverse effects.

5.4 Drug Accountability

Patients will be instructed to bring empty bottles of study drug at the final visit. Adherence with the prescribed study treatment regimen will be determined by reviewing the study diary and returned bottles.

5.5 General Concomitant Medication and Supportive Care Guidelines

There will be no restrictions on concomitant medications or supportive care measures.

All subjects will be treated with fluconazole 200 mg tablets once-a-week dosing for prophylaxis as topical steroid therapy may increase the risk of candidiasis. This is typically very effective at preventing candidiasis in susceptible patients, and since there are no interim clinical visits, this will minimize the risk of secondary infection, which if not detected early, could confound the results at the week 4 evaluation. A single weekly dose of fluconazole is not sufficient to have an impact on therapeutic levels of other medications. Fluconazole is a pregnancy category D drug. A such, pregnant women will be excluded from this study.

Any subjects that are already taking a systemic antifungal medication at the time of study enrollment will continue their prescribed medication and will not need to take the additional weekly fluconazole dose.

Clotrimazole or nystatin will be prescribed as an alternative antifungal drug in the event of fluconazole

CONFIDENTIAL

This document is confidential. Do not disclose or use except as authorized.

allergy. Clotrimazole 10 mg troche (lozenge) to be dissolved in the mouth four times a day for four weeks; or nystatin 100,000 unit/mL oral suspension to rinse for one minute, swish and spit, four times a day for four weeks.

Possible side effects of fluconazole include nausea, vomiting and headache. Possible side effects of nystatin oral suspension include rash, diarrhea, nausea, oral irritation, vomiting. Possible side effects of clotrimazole troche (lozenge) include abnormal sensation in the mouth, loss of appetite, diarrhea, nausea, vomiting, abnormal liver function tests.

5.6 Criteria for Taking a Participant Off Protocol Therapy

Subjects will be taken off protocol therapy for any of the following reasons:

- If the principal investigator feels it is in their best interest
- If the subject cannot tolerate the study rinses
- Intercurrent illness that prevents further administration of treatment
- Unacceptable adverse event(s)
- Participant demonstrates an inability or unwillingness to comply with the oral medication regimen and/or documentation requirements
- Participant decides to withdraw from the protocol therapy
- General or specific changes in the participant's condition render the participant unacceptable for further treatment in the judgment of the treating investigator

Participants will be removed from the protocol therapy when any of these criteria apply. The reason for removal from protocol therapy, and the date the participant was removed, must be documented in the case report form (CRF). Alternative care options will be discussed with the participant.

Subjects may be removed from the study in favor of clinical care should their symptoms worsen or should they have an adverse reaction to the study drug.

In the event of unusual or life-threatening complications, treating investigators must immediately notify the Overall PI [name], PhD, MPH at [contact] ([name]).

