2.1 Study Design

This is a single center, 4-week, open label randomized, phase II study. Randomization will be conducted by the BWH Investigational Pharmacy. The study period will be four weeks, which based on previous studies should be an adequate period to assess significant clinical improvement. Subjects will be evaluated clinically at baseline before starting treatment and at the end of the four-week period, for a total of two visits. Subjects will be randomized to either compound dexamethasone in Mucolox™ or dexamethasone only. Subjects will return for evaluation after four weeks at which time the primary end-points will be assessed.

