5.8 Criteria for Taking a Participant Off Study

Participants will be removed from study when any of the following criteria apply:

- Lost to follow-up
- Withdrawal of consent for data submission
- Death

The reason for taking a participant off study, and the date the participant was removed, will be documented in the case report form (CRF).

6. BIostatistical Analysis

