6.1 Study design/Endpoints

The primary objective of this open label randomized phase II study is to evaluate the efficacy and tolerability of topical compound dexamethasone solution in a Mucolox™ for the treatment of oral lichen planus. The primary endpoint will be a change from pre to post treatment in each subject's subjective sensitivity score (0-10) evaluated at baseline and 4 weeks post treatment for each arm. We will also compare changes of the daily subject's subjective sensitivity score (0-10) over time for each arm.

The secondary objectives include the evaluation of objective data using the REU scoring system and the oral health related quality of life using the 24-item Chronic Oral Mucosal Diseases Quality of Life Questionnaire. For the analysis of secondary endpoints see section 6.5.

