6.2 Sample Size, Accrual Rate and Study Duration

The sample size was calculated based on the data by Rhodus et al., as to ensure at least 80% power and two-sided alpha of 0.05 in detecting a t difference of 2.0 points oral pain on an 11 point scale (VAS 0-10) between Arm A and B²⁴. The mean expected change for Arm A will be 6.5 points reduction with a standard deviation of 1.4 points. The mean expected change for Arm B will be 4.5 points reduction with a standard deviation of 1.4 points.

A total of 12 patients per arm will be enrolled (total of 24 subjects). The proposed sample size includes a loss of follow up of 5%. Approximately 75 patients per year are diagnosed with oral lichen planus at the Division of Oral Medicine and Dentistry (BWH)³². We anticipate the accrual rate will be approximately 5 patients per month, thus the accrual goal will be achieved in approximately five months.

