6.3.2 Protocol Review and Amendments

This protocol, the proposed informed consent and all forms of participant information related to the study (e.g., advertisements used to recruit participants) and any other necessary documents will be submitted, reviewed and approved by a properly constituted IRB governing each study location.

Any changes made to the protocol will be submitted as amendments and will be approved by the IRB prior to implementation. Any changes in study conduct will be reported to the IRB. The BWH Overall Principal Investigator will disseminate protocol amendment information to all participating investigators.

All decisions of the IRB concerning the conduct of the study will be made in writing.

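### Section 5.6 allows removal from the study for worsening or an adverse reaction, grounds that 5.8 does not list; if applied before about Day 23, no post-baseline tolerability, REU or COMDQLQ assessment is scheduled

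*Combined protocol and SAP*

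**What the plan says.** Three places in the combined protocol and SAP govern a patient who worsens or reacts badly.

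- Section 5.6 (off protocol therapy) lists grounds for ending therapy, including intolerance of the rinses and unacceptable adverse events. It requires the reason and date to be recorded, then adds: "Subjects may be removed from the study in favor of clinical care should their symptoms worsen or should they have an adverse reaction".
- Section 5.8 (off study) opens "Participants will be removed from study when any of the following criteria apply" and lists loss to follow-up, withdrawal of consent for data submission, and death. Worsening and adverse reactions are not among them.
- Section 5 says that if worsening requires a new immunomodulatory drug, "patients will remain on treatment, but will be regarded as unevaluable for the primary endpoint".

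On timing, section 2.1 has patients assessed at baseline and "at the end of the four-week period, for a total of two visits". The section 5 schedule gives the second visit a window of Day 28 ± 5 days. Section 5.5 confirms that there are no interim visits, and section 5.7 that there is no follow-up. Comfort (item 7), taste (item 8) and overall change (item 10) appear only on the Visit 2 form in Appendix 4. Post-treatment worst sensitivity and REU are also taken at that visit. COMDQLQ is scheduled there too, although section 5.1.2 describes its second completion as falling at the end of treatment.

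Section 6.1 also plans to compare changes in the daily "subjective sensitivity score (0-10) over time for each arm". The diary that holds this score is reviewed at the week 4 visit (sections 6.6 and 10.1).

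**The concern.** The protocol separates leaving therapy from leaving the study, then blurs the line for the patients who say most about tolerability. An investigator who follows the 5.6 sentence literally on, say, Day 10 ends that patient's participation with no further assessment scheduled. The diary score stops at removal, and no early retrieval of the diary is stated.

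The patients lost this way are lost because they worsened or reacted badly. Tolerability is named in the primary objective (sections 2.2 and 6.1) and in the hypothesis (section 2.4). Removal is at the investigator's discretion in an open-label trial, so it could differ between arms. Three sets of results are exposed: the descriptive comfort, taste and global-change ratings, for which section 6 plans no test; the between-arm REU comparison in section 6.5; and the within-arm COMDQLQ changes in the same section. Each would rest mainly on patients who got on with the rinse. Section 6.6 names only low use and new immunomodulatory drugs as reasons for replacement, and only in relation to the primary endpoint.

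**Working it through.** **Planned size.** Section 6.2 gives a difference of 2.0, SD 1.4, two-sided alpha 0.05, at least 80% power, 5% loss to follow-up and 12 per arm.

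- Normal approximation: n = 2 × (1.96 + 0.84)² × 1.4² / 2.0² = 7.7, so 8 per arm. The exact t-test needs 9 (power 0.812), and 9/0.95 = 9.5, so 10 per arm.
- Section 6.4 also allows the Mann-Whitney test. At its worst-case efficiency of 0.864, 9/0.864 = 10.4, so 11; 11/0.95 = 11.6, so 12 per arm, the planned figure.
- Power by t-test is 0.917 at 12 v 12, 0.904 at 11 v 12 and 0.887 at 10 v 12. Lost numbers cost little, so power is not the issue.

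**When data are lost.** The window opens on Day 28 − 5 = Day 23. From then on Visit 2 can be done within window. Before then, nothing is scheduled.

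| Kept | Not scheduled |
|---|---|
| Baseline worst sensitivity, REU and COMDQLQ | Post-baseline worst sensitivity, REU and COMDQLQ |
| Reason and date of stopping (5.6) | Comfort and taste (Visit 2 items 7 and 8) |
| Adverse events up to removal; SAEs to 30 days after last dose (6.6.1, 10.6, 10.8) | Global change (Visit 2 item 10) |
| Diary up to removal, if returned | Diary after removal |

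**Shift in an arm mean.** Let k of 12 patients be removed, and let the remaining patients' mean exceed the removed patients' mean by g. The mean over all 12 is [(12 − k)·m + k·(m − g)]/12 = m − (k/12)·g, where m is the remaining patients' mean. The observed mean is therefore off by (k/12)·g. If the removed patients are replaced, 12 + k are randomised and 12 observed, so the shift is k/(12 + k)·g.

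The documents give neither k nor g. The 5% in section 6.2 is loss to follow-up (0.05 × 12 = 0.6 patients per arm), not a removal rate. As assumptions, take k = 1 to 3 and g = 0.5 to 1.5 SD:

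| k | Share of gap, unreplaced | Share of gap, replaced | Unreplaced shift (SD) | Replaced shift (SD) |
|---|---|---|---|---|
| 1 | 8.3% | 7.7% | 0.04–0.13 | 0.04–0.12 |
| 2 | 16.7% | 14.3% | 0.08–0.25 | 0.07–0.21 |
| 3 | 25.0% | 20.0% | 0.13–0.38 | 0.10–0.30 |

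**Illustration for REU.** Assume further that removals occur in one arm only, are not replaced, and that there is no true difference. In SD units the standard error of the arm difference is √(1/(12 − k) + 1/12). The two-sided rejection rate comes from the noncentral t with 22 − k degrees of freedom and noncentrality equal to shift/SE.

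| k | SE | Shift/SE | Rejection rate at nominal 5% |
|---|---|---|---|
| 1 | 0.417 | 0.10–0.30 | 5.1–5.9% |
| 2 | 0.428 | 0.19–0.58 | 5.4–8.6% |
| 3 | 0.441 | 0.28–0.85 | 5.8–12.8% |

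If removals are alike in number and gap in both arms, the shift cancels from the between-arm REU comparison. It does not cancel from results described or tested within an arm.

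**The case against.** The strongest reply is that the sentence means stopping therapy only. It sits under a heading about protocol therapy, follows a remark on alternative care, and is contradicted by 5.8. That reading is plausible. But the sentence says study, not therapy, and even on the narrower reading no passage expressly requires patients who stop to be assessed at Day 28. The rewording would simply make the intent explicit.

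Second, the loss is inferred from silence. Nothing forbids bringing Visit 2 forward, and section 5.1.2 could be taken to cover COMDQLQ at an early stop. That stands as a limit on the claim: data need not be lost, but nothing requires their collection, so practice would vary by investigator.

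Third, the most direct tolerability evidence survives in the adverse events and the reason for stopping. Section 2.2 measures its objective by symptom reduction, and comfort and taste have no named endpoint role. This is correct and keeps the point small. It does not supply the missing ratings, REU or COMDQLQ.

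A reader might also infer that the primary comparison is materially biased. The documents do not support that. Low use for more than two weeks and new immunomodulatory drugs already make a patient unevaluable and replaced (section 6.6). How many removed patients would fall outside those rules cannot be worked out, because section 6.6 judges compliance from a diary review at the week 4 visit, which a removed patient would not have.

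**Conclusion.** The inconsistency between 5.6 and 5.8 is real. Applied as written before about Day 23, the sentence leaves a patient with no scheduled post-baseline assessment, for a reason tied to tolerability or worsening. The descriptive tolerability results, the between-arm REU comparison and the within-arm COMDQLQ changes could then lean toward patients who tolerated the rinse.

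The size is unknown and may be zero. The firm figure is arithmetic: each unreplaced removal moves a 12-patient arm mean by 8.3% of the gap between removed and remaining patients. Someone might read the 12.8% rejection rate as an expected error rate. It is not: it needs three removals in one arm, none in the other, no replacement, a 1.5 SD gap and no true difference, and the documents give neither a removal rate nor an SD for REU. This is a cheap improvement, not a flaw that undermines the trial.

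**What to change.** Reword the 5.6 sentence along these lines: worsening or an adverse reaction may end protocol therapy in favour of clinical care, but does not by itself end study participation; off-study reasons are those in 5.8, and new immunomodulatory drugs are handled as in section 5. Then:

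- When the rinse stops, complete Visit 2 items 7 and 8, noting whether in person or remotely, and collect the diary. Section 5.4 already relies on it: "Adherence with the prescribed study treatment regimen will be determined by reviewing the study diary and returned bottles".
- Keep the scheduled Day 28 assessment (worst sensitivity, global change, REU, COMDQLQ) unless consent is withdrawn.
- Leave the section 6.6 evaluability rules unchanged.
- Flag patients who stopped therapy and any alternative care they received, and show REU and COMDQLQ with and without them.

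The cost is one amendment under section 6.3.2 ("Any changes made to the protocol will be submitted as amendments and will be approved by the IRB prior to implementation"): a reworded sentence, two cross-references and one extra use of an existing form page per patient who stops. A few such patients would be asked to attend a visit already on their schedule, and some comfort and taste ratings would be given remotely. Their Day 28 scores will partly reflect alternative care rather than the rinse, which is why results are shown both ways.

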5.7 Duration of Follow Up

There is no follow-up period after completing the four-week treatment period.

CONFIDENTIAL

This document is confidential. Do not disclose or use except as authorized.

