7. DOSING DELAYS/DOSE MODIFICATIONS

All adverse events experienced by participants will be collected from the time of the first dose of study treatment, through the study and until the final study visit. Participants continuing to experience toxicity at the final study visit may be contacted for additional assessments until the toxicity has resolved or is deemed irreversible.

There will be no dosing delays/modifications.

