10.6 Expedited Adverse Event Reporting

10.6.1 Investigators will report to the Overall PI any serious adverse event (SAE) that occurs after the initial dose of study treatment, during treatment, or within 30 days of the last dose of treatment on the local institutional SAE form.

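### Serious adverse events are reportable to 30 days after the last dose, but no contact is scheduled after the final visit, so later events are found only if participants report them

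*Combined protocol and SAP*

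**What the plan says.** - **Section 10.6.1** obliges investigators to tell the Overall PI of any SAE that occurs after the first dose, "during treatment, or within 30 days of the last dose of treatment on the local institutional SAE form".
- **Section 5.7** states: "There is no follow-up period after completing the four-week treatment period".
- **Section 7** collects adverse events "from the time of the first dose of study treatment, through the study and until the final study visit". It adds that participants whose toxicity is continuing at that visit may be contacted until it resolves or is judged irreversible.
- **Section 5** has subjects evaluated at baseline and "at the end of the four-week period, for a total of two visits". The visit table places the second visit at Day 28 with a margin of 5 days either side.
- **Section 5.2** gives the treatment length as "28 days (4 weeks) One Cycle Only".
- **Sections 6.3.1, 10.1 and 12.1** rely on participants coming forward. Section 6.3.1 asks them to tell study staff about adverse events as these occur. Sections 10.1 and 12.1 ask them to contact the treating physician about side effects that are unexpected or last more than 7 days. Section 10.1 names phone, email and the patient portal. None of the three sections gives an end date.

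**The concern.** The protocol sets a safety window that outlasts every planned point of enquiry. Investigators can report only what they learn of, and after the final visit nothing in the schedule prompts anyone to ask. A participant admitted to another hospital in the following month, who sees no link to a mouth rinse, has no planned occasion to mention it.

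What is at stake is the completeness of the SAE data. Tolerability is part of the primary objective (Sections 2.2 and 6.1), so safety ascertainment is not a side issue here. Any summary of SAEs to 30 days after the last dose would mix two kinds of data: events asked about up to the final visit, and events volunteered afterwards. Treatment is open label, and the PI or covering clinician judges relatedness (Section 6.3.1). Volunteering and attribution could therefore differ between arms, though nothing in the documents shows that they would.

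**Working it through.** The documents give no figure for the share of the window covered by planned enquiry, so there is none to reproduce. The check is a day count.

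**Inputs**
- SAE window: first dose to 30 days after the last dose (Section 10.6.1).
- Treatment: 28 days, one cycle (Section 5.2).
- Last scheduled enquiry: the final visit, Day 28 ± 5, so day 23 to day 33 (Section 5).
- Scheduled follow-up after treatment: none (Section 5.7).

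**Formulas**
- Window length = last-dose day + 30.
- Days after the last scheduled enquiry = window length − visit day.
- Share = days after the last scheduled enquiry ÷ window length.

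Dosing is assumed to stop no later than the final visit, because unused supply is then to be returned (Sections 11.1.9 and 11.2.10). For a late visit, two cases are shown: dosing to the visit, and dosing stopped at day 28.

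| Final visit | Last dose | Window (days) | Days after last enquiry | Share |
|---|---|---|---|---|
| Day 23 | Day 23 | 23 + 30 = 53 | 53 − 23 = 30 | 30/53 = 56.6% |
| Day 28 (nominal) | Day 28 | 28 + 30 = 58 | 58 − 28 = 30 | 30/58 = 51.7% |
| Day 33 | Day 33 | 33 + 30 = 63 | 63 − 33 = 30 | 30/63 = 47.6% |
| Day 33 | Day 28 | 28 + 30 = 58 | 58 − 33 = 25 | 25/58 = 43.1% |
| Day 28, early stop (illustration) | Day 14 | 14 + 30 = 44 | 44 − 28 = 16 | 16/44 = 36.4% |

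The share reaches exactly half with a visit on day 30 if dosing runs to the visit (30/60), or on day 29 if dosing stopped on day 28 (29/58). Later visits bring it below half.

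**What covers those days**
- The optional contact in Section 7 requires toxicity already present at the final visit. It cannot detect an event that starts later.
- Self-reporting under Sections 6.3.1, 10.1 and 12.1 has no end date and so can reach into the period. It depends on the participant, and none of these sections mentions the 30 days or asks staff to enquire.
- The treatment diary in the appendix ends at day 28.

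A new SAE after the final visit can therefore reach the investigator, but only if someone volunteers it.

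**The case against.** The strongest reply is that the sections can be read together. Section 10.6.1 places a duty on investigators to report SAEs and does not promise active enquiry for 30 days. Section 7 governs routine collection of all adverse events, and Section 5.7 governs study follow-up. A duty to pass on SAEs that become known can reasonably outlast the visits. This stands: the text can be followed without breach. It does not say how late SAEs would become known, and that gap remains.

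A reader might also infer that there is no contact at all after week 4 and that the post-treatment period is unobserved. The documents do not support that. Section 7 permits contact for continuing toxicity, and three sections provide open-ended self-reporting. The accurate description is that no contact is scheduled and observation is passive.

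A reader might equally say that more than half of the window is uncovered. That holds on the nominal schedule, but narrowly, and not across the whole visit window. Nor is the measure simply days without scheduled contact: with only two visits, that would describe almost all of the window. The relevant quantity is days after the last scheduled enquiry.

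Finally, the protocol expects no significant systemic absorption and no systemic side effects (Sections 8.1 and 10.4), plans no between-arm comparison of SAEs, and does not tie its toxicity stopping rule (Section 6.6.1) to the 30-day window. These points limit the consequence. They do not supply a way of finding late events.

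**Conclusion.** The point holds as a gap in SAE ascertainment. The reporting window runs to 30 days after the last dose, and the planned enquiry stops at the final visit. About half of the window lies beyond that visit: 52% nominally, 43% to 57% across the permitted visit dates, and less after early stopping (36% in the illustration). In that stretch new SAEs are captured by spontaneous report only, so the count may be incomplete.

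The range assumes that dosing ends at the final visit or at day 28, and that a participant who stops early still attends. How many SAEs would be missed cannot be estimated, since the documents give no expected SAE rate. Different reporting by arm is a possibility in an open-label trial, not a demonstrated bias. The primary endpoint and the sample size are not affected. The point merits correction because the remedy is cheap and tolerability belongs to the primary objective.

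**What to change.** 1. Add one scheduled contact for every treated participant about 30 days after the last dose, by phone, email or patient portal as in Section 10.1, asking both arms the same short question about SAEs. Include participants who stopped early or are unevaluable for the primary endpoint, since all are evaluable for toxicity from first treatment (Section 6.6.1).
2. Record the answer on forms the plan already has: the institutional SAE form (Section 10.6.1) and the toxicity case report forms (Section 10.8).
3. Reconcile Sections 5.7, 7 and 10.6.1 so that they state one post-treatment safety period and how SAEs within it are identified.
4. If no contact is added, state in the report that SAEs after the final visit were captured by spontaneous report only.

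The cost is one short contact for each of about 24 participants, slightly more if patients are replaced under Section 6.6, plus a wording amendment. It needs no new visit and no change to treatment or endpoints.
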